### 5.8 Analysis of drop-outs

Of randomized subjects who attended baseline exam and commenced study treatment (i.e. attended V3), we will detail the number (total and per study treatment group) who completed vs dropped out after V3. The definition of drop-outs are subjects attending V3 but dropped out without at least one additional study fasting glucose measurement either at V6 or V8. Baseline characteristics for the intention to treat population will be provided for both intervention and control subjects and will be separated by drop-outs.

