#### Intention to treat

The “Intention-to-Treat” population: all randomized study subjects with at least two during study fasting plasma glucose measurements will be analyzed in intention to treat analysis (i.e. regardless of any protocol deviations). This analysis set includes the evaluation of primary and secondary outcomes as well as adverse events (AE) and serious adverse events (SAE) between intervention and control group.

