## 5 Planned analyses

### 5.1 Status of subjects, protocol deviations and population definition

#### 5.1.1 Status of subjects

The number of subjects will be provided for the following groups:

- Subjects who attended V2 and fulfilled low water intake criteria (based on urine volume, urine osmolality and plasma copeptin) were randomized. We will thus detail numbers of subjects randomized (total and in intervention and control groups, respectively).
- Of those who were randomized at V2, not all appeared to visit 3, where a baseline clinical examination was performed and therapy (intervention or control) commenced. Thus, number

(total and per intervention/control group) who commenced therapy will be detailed next, including the number and percentage who dropped out between randomization (V2) and baseline exam/start of study (V3) in total and per study treatment group.

- We will detail the numbers who were present at V3, V6 and V8 (totally and per study treatment group).
- We will detail the numbers who completed the study for the intention to treat analysis (i.e. subjects randomized who underwent baseline exam/commenced the study treatment and had at least one additional measurement of fasting glucose (at V6 or V8), in total and per study treatment group).
- Of randomized subjects who attended baseline exam and commenced study treatment (i.e. attended V3), we will detail the number (total and per study treatment group) who dropped out after V3 without at least one additional study fasting glucose measurement (i.e. not completed subjects).

The current numbers at early visits (V2-3) and preliminary numbers on late visits (V6) are given in the section above.

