### 5.1.3 Populations

We expect a final study sample for intention to treat analysis of at least n=544 evaluable study subjects who have completed the protocol (i.e. with at least 2 fasting glucose measurements, meaning at V3 and at either V6 or V8 or at both V6 and V8). We expect a dysbalance in the final study sample (46% intervention vs 54% control therapy) due to dysbalance in the drop-out rate between intervention and control groups.

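### As written, the SAP 5.8 table cannot show the baseline profile of drop-outs: the intention-to-treat set excludes them by definition, and V6-only participants count as completed

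*SAP*

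**What the plan says.** Section numbers are those in the body of the SAP.

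- **ITT set (4.1):** "all randomized study subjects with at least two during study fasting plasma glucose measurements will be analyzed in intention to treat analysis". Section 5.1.3 spells this out: "with at least 2 fasting glucose measurements, meaning at V3 and at either V6 or V8 or at both V6 and V8".
- **Drop-outs (5.8):** "The definition of drop-outs are subjects attending V3 but dropped out without at least one additional study fasting glucose measurement either at V6 or V8".
- **Completed (5.1.1):** those who started treatment and "had at least one additional measurement of fasting glucose (at V6 or V8), in total and per study treatment group". A V6 value alone is therefore enough.
- **Drop-out table (5.8):** "Baseline characteristics for the intention to treat population will be provided for both intervention and control subjects and will be separated by drop-outs".
- **Other baseline tables (5.2, 5.3):** assigned to the ITT and per-protocol sets only.
- **Planned counts (5.1.1):** "We will detail the numbers who were present at V3, V6 and V8 (totally and per study treatment group", as well as numbers randomised, lost between V2 and V3, and dropped out after V3, each by arm.
- **Expected loss (5.1.3):** "We expect a dysbalance in the final study sample (46% intervention vs 54% control therapy) due to dysbalance in the drop-out rate" between the arms. Section 6.3 places the imbalance after V3 and describes loss between V2 and V3 as balanced.
- **Primary outcome and model (5.6.1, 5.6.2):** the 12-month change in fasting glucose, from a mixed model of the 6- and 12-month changes that relies on data being missing at random.

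**The concern.** The table is the SAP's only planned description of what kind of participant was lost after treatment began. It is specified on a set from which those people have already been removed. A programmer following 5.8 literally would produce an empty column, and any repair made after the results are known would be a post-hoc choice.

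The labels hide a second group. Someone who gives a V6 sample and leaves in month 7 lacks the value that the primary outcome needs, yet is reported as completed and never enters the drop-out analysis.

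This matters more here than in a trial with equal loss. The SAP already expects more loss in the water arm, and its primary model assumes missing at random. A reader will want to see whether those lost differed at baseline from those kept, and whether the pattern differed by arm.

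**Working it through.** **1. The plan's own figure.** Inputs from SAP 3.3: difference 0.14 mmol/L, SD 0.58 mmol/L, two-sided 0.05, power 80%. From 5.1.3: split 46:54.

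- Equal arms: n = 2 × (1.960 + 0.842)² × 0.58² / 0.14² = 2 × 7.849 × 17.163 = 269.4, so 270 per arm and 540 in total, as stated.
- Split 46:54: N = 7.849 × 17.163 / (0.46 × 0.54) = 134.71 / 0.2484 = 542.3. Rounded up by arm, this is 250 + 293 = 543, against 544 stated. Power at 544 with this split is 80.1%.

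The 544 and the split are consistent, so they are used below as the expected ITT set.

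**2. The definitions side by side.** A drop-out has no fasting glucose at V6 or V8, so at most one value (V3). The ITT set needs two. For those with a V3 value:

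| V6 value | V8 value | ITT (4.1, 5.1.3) | Drop-out (5.8) | Label (5.1.1) |
|---|---|---|---|---|
| no | no | no | yes | not completed |
| yes | no | yes | no | completed |
| no | yes | yes | no | completed |
| yes | yes | yes | no | completed |

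None of the four patterns without a V3 value falls in both sets either. (V6 plus V8 without V3 meets the wording of 4.1 but not of 5.1.3; it is not a drop-out under 5.8.) Overlap is 0 of 8 patterns, so the drop-out columns of an ITT table are empty in both arms.

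**3. Size of the group left out.**

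- Water: 0.46 × 544 = 250. Control: 0.54 × 544 = 294.
- Randomisation is 1:1 and loss between V2 and V3 is described as balanced, so take equal numbers at V3 (assumption). Relative retention is then 0.46 / 0.54 = 0.85.
- The number at V3 is not in the text available. SAP 5.1.1 refers to visit numbers given elsewhere, which may lie in a figure not shown. The table therefore gives a range. With control retention r, V3 per arm = 293.76 / r; drop-outs are that figure minus 293.76 (control) or 250.24 (water).

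| Control retention (assumed) | Water retention | V3 per arm | Drop-outs, water | Drop-outs, control | Overall loss |
|---|---|---|---|---|---|
| 100% | 85% | 294 | 44 | 0 | 7% |
| 95% | 81% | 309 | 59 | 15 | 12% |
| 90% | 77% | 326 | 76 | 33 | 17% |
| 80% | 68% | 367 | 117 | 73 | 26% |

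For reference, the protocol's sample-size section anticipates loss of up to 20%. Applied from V3, that gives 544 / 0.80 = 680, or 340 per arm: 340 − 250 = 90 water and 340 − 294 = 46 control drop-outs.

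**4. V6-only participants.** The documents give no figure. Each 1% of the ITT set is 0.01 × 544 = about 5 people labelled completed without a 12-month value. Attendance counts do not identify them: the number at V6 minus the number at V8 equals V6-only minus V8-only attenders, so it shows net loss.

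**The case against.** The best case for the plan has four parts.

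**Intent.** Section 5.8 opens with everyone who attended V3 and counts completed versus dropped out among them. Its last sentence may have meant ITT characteristics shown apart from those of drop-outs. That is probably right, and baseline data exist for V3 attenders. It makes this a correction of wording, but the sentence still names the wrong set and no other section supplies the table.

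**What is already planned.** A reader might infer that withdrawals from the water arm cannot be characterised at all. The documents do not support that. Counts and attendance by arm are planned (5.1.1, 5.8), and adverse events are to be reported for all V3 attenders and compared by arm (5.7.3). The protocol has staff ask about tolerance of the water at visits and in telephone contacts. This stands and narrows the gap to the baseline comparison. One reservation: SAP 4.1 assigns the adverse-event evaluation to the ITT set, which would leave out drop-outs, so 4.1 and 5.7.3 should be reconciled.

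**Missing at random.** A baseline table cannot verify this assumption, which concerns unobserved values. The scenario data sets in 6.3, with more and less pessimistic values for unobserved measurements, address it more directly. This also stands. The table would describe who was lost and help in choosing sensible scenarios.

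**The estimate.** V6-only participants stay in the mixed model with their 6-month change. Calling them completed does not change the 12-month estimate. This stands too.

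**Conclusion.** The point holds in a limited form. By definition alone, with no assumption, the 5.8 table has no drop-outs in either arm, and V6-only participants are classed as completed although the primary outcome is at 12 months. What the plan lacks is a baseline comparison, by arm, of those lost after V3, with those lost between V6 and V8 shown separately.

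The relative retention of 0.85 rests on equal arms at V3. The absolute counts, from 44 versus 0 up to 117 versus 73, rest in addition on assumed control retention and are indicative only.

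Two further inferences go beyond the documents. The SAP expects unequal loss but never attributes it to poor tolerability of the water, so the imbalance should not be read as an established tolerability signal. Nor does the empty column show that the primary estimate is biased, since no estimate or test depends on this table. It should be corrected before the data are analysed, as a planned description that cannot give its intended result.

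**What to change.** - **Table in 5.8:** replace the ITT set with all randomised subjects who attended V3. Show baseline characteristics by arm for three groups: no post-baseline fasting glucose, V6 only, and V8 present. Add this set to the table specifications in 5.2 and 5.3 for this purpose.
- **Labels in 5.1.1, 5.1.3 and 5.8:** call those with V3 plus V6 or V8 *evaluable*, and reserve *completed* for those with a V8 fasting glucose. Change all three sections together, or a new inconsistency results.
- **Leavers:** report time of leaving by arm, and the reason where one was recorded. The documents do not show that reasons for withdrawal are collected, so this column may be incomplete; show the rest as unknown.
- **Unchanged:** the ITT set, the primary model and the scenario analyses in 6.3.

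The cost is SAP wording and one extra table, with no new measurements. The downside is that the stated completion figure falls by the number of V6-only participants.

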## 6 Statistical analyses

### 6.1 Hypothesis and significance level

- The primary and secondary outcomes will be tested using two-sided tests ( $P<0.05$ ) with the hypothesis that there will be a significant difference in the change of the outcome parameter between intervention and control group at  $P<0.05$  level in a 2-sided test.

## 6.2 Distributions and normality assessment

For normally distributed data we will use parametric tests. If a variable deviates from normal distribution, we will log transform the variable. If the variable still deviates from normal distribution, we will use a non-parametric test.

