**OR Delta 24h UVol (Baseline vs. 3 months, 6 months, 9 months and 12 months):**

- Control Group: Those with an increase in delta 24h UVol not greater than 500 mL from baseline.
- Intervention group: Those with an increase in delta 24h UVol of at least 1000 mL from baseline.

Furthermore, all individuals attending a clinic study visit (V3, V6 or V8) in a non-fasted state will be excluded from the per protocol analyses. Some other protocol deviations let to exclude patients are detailed in Section 5.1.2

Missing data

Missing data on outcomes (i.e. change of fasting glucose and the secondary cardiometabolic measures) will not be imputed, so subjects with missing data on outcome parameters will not be included in analysis of the respective outcome. For each of the outcomes, the maximum number of subjects will be included (e.g. if there are n=544 evaluable subjects for fasting glucose change, all of these will be included even if there are less evaluable subjects for any other cardiometabolic outcome parameter).

Given the randomized nature of the study, we will not perform any adjustments (which in turn can be affected by missing data on the covariates adjusted for) with three exceptions: (1) As detailed in “statistics” we will include adjustment for the baseline value of the outcome parameter in question (e.g. the change of glucose outcome will be adjusted for the baseline value of glucose). The motif of this adjustment is to minimize bias related to regression towards the mean. (2) As the randomization is stratified by sex, this covariate will be included in all outcome analyses. (3) If clinically significant/meaningful treatment group differences appear in baseline values of age, BMI or diabetes status in any outcome analysis, we will add a sensitivity outcome analysis in which we adjust for such baseline differences. Any missing values for these covariates will be imputed to obtain the same number of evaluable subjects in non-adjusted and adjusted analyses. The technique we propose is Multiple Imputation by Chained Equations (MICE) with subsequent application of Rubin’s rule to combine results from different imputations. We will base the analyses on 20-30 imputed data sets. For this analysis we will use SAS PROC MI in combination with PROC MIXED/PROC GLM and PROC MIANALYZE.

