## 5.6 Analysis of primary criteria

### 5.6.1 Description of primary outcome measure

The primary outcome measure is between group comparison of the change from baseline to 12-month of fasting plasma glucose.

Variable name	Variable source 	Type 	Unit	Set 
Change of fasting plasma glucose from baseline to 6-and 12-months	D	C	mmol/L	ITT, PP

2. *(R)aw or (D)erived data*
4. *(C)ontinuous or (O)rdinal or (N)ominal*
5. *Intention to treat (ITT) or Per Protocol (PP)*

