### 5.6.2 Analysis of primary outcome parameters

The primary analysis (intention-to-treat) will compare the between study groups (intervention vs control treatment) LS-means differences on the changes from baseline to 12 months and from baseline to 6 months in fasting plasma glucose. The main analysis will be based on a linear mixed model with fasting plasma glucose change from baseline to study visits where it is measured during the study (6 and 12 months) as dependent variable. This model produces unbiased estimates under the assumption that missing data are missing at random. The model will be adjusted (through fixed effects) for sex (because of the stratified randomization), baseline value of fasting plasma glucose, treatment, study visit and interaction between treatment and study visit. We will in the mixed regression analysis model within-patient correlation to decrease exponentially with number of days between measurements or through an AR(1) model. The choice of correlation structure specifies the variance-covariance matrix in the mixed regression model. The choice of covariance structure rests on principles of parsimony, simplicity and prior beliefs, rather than post-analysis testing. Model assumptions will be assessed through visual inspection of plots of suitable regression residuals. The estimated LS-mean differences between treatment levels for the change in fasting plasma glucose from baseline to 12 months and baseline to 6 months, the corresponding 95% confidence intervals (CIs) and p-values will be provided. The same analyses will be conducted on the imputed data set (see “Missing Data” sub-section under section 4.1) and the per protocol data set. The analyses will be conducted using SAS PROC MIXED.

Sensitivity analysis as described in Section 4.1, part “Missing Data” could be performed. Conclusions regarding the inclusion of baseline characteristics in the linear mixed model will be based on clinical significances.

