### 5.7.1 Description of secondary criteria

Variable name and unit	Variable source 	Type 	Set 
Diabetes			
Diabetes incidence after baseline visit during 12 months	R	N	ITT, PP
Change from baseline to 6 and 12 months of cardiometabolic risk factors			
Fasting and 2h glucose (during OGTT) (mmol/L)	D	C	ITT, PP
Fasting and 2h insulin (during OGTT) (mIE/L)	D	C	ITT, PP
Fasting HbA1c (mmol/mol)	D	C	ITT, PP
Fasting cortisol (nmol/L)	D	C	ITT, PP
Fasting ACTH (pmol/L)	D	C	ITT, PP
Fasting Apo A1 (g/L)	D	C	ITT, PP
Fasting ApoB (g/L)	D	C	ITT, PP
Fasting Triglycerides (mmol/L)	D	C	ITT, PP
Fasting LDL (mmol/L)	D	C	ITT, PP
Fasting HDL (mmol/L)	D	C	ITT, PP
C-reactive protein (mg/L)	D	C	ITT, PP
Creatinine (μmol/L)	D	C	ITT, PP
eGFR (mL/min/1,73 m  )	D	C	ITT, PP
BMI (Kg/m  )	D	C	ITT, PP
Waist circumference (cm)	D	C	ITT, PP
Systolic blood pressure (mm Hg)	D	C	ITT, PP
Diastolic blood pressure (mm Hg)	D	C	ITT, PP
Body fat%	D	C	ITT, PP
Other blood laboratory parameters			
Fasting copeptin (pmol/L)	D	C	ITT, PP
Urine laboratory parameters			
Albumin/creatinine ratio (g/mol)	D	C	ITT, PP

1. (R)aw or (D)erived data
2. (C)ontinuous or (O)rdinal or (N)ominal
3. Intention to treat (ITT) or Per Protocol (PP)

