### 5.7.2 Analysis of secondary outcome parameters

New-onset diabetes is defined as 2 consecutive fasting plasma glucose values  $\geq 7.0$  mmol/L or 2-hour post OGTT value of  $\geq 11.0$  mmol/L after the baseline exam (V3). In addition, new onset diabetes is considered present if diagnosed by a physician outside of the current study, as assessed in the questionnaire (answering yes on having had a physician diagnosis of diabetes or having been prescribed

medication for diabetes) after the baseline exam (V3). All individuals with a diagnosis of diabetes at or before the baseline exam (V3) will be excluded in the analysis of incidence of diabetes.

The difference in diabetes incidence between the intervention and control group will be analyzed using logistic regression with diabetes incidence as the binary outcome and treatment arm as exposure variable and reported as the odds ratio (OR) including 95 % CI for diabetes incidence in intervention vs control. As the randomization should lead to no difference in diabetes risk factors, the main analysis will only be adjusted for sex (as the randomization is stratified by sex, this covariate will be included in all outcome analyses), but we will also add a sensitivity analysis to adjust for key diabetes risk factors at baseline (fasting glucose, diabetes status, BMI, age), if there is a clinically significant difference in these factors between treatment groups despite the randomization.

Cardiometabolic risk factors will be analyzed using the same method as for the primary outcome, but with baseline value for the actual factor as a covariate instead of baseline value of fasting plasma glucose.

In addition, to assess the possible association between change in fasting plasma glucose levels, copeptin, other cardiometabolic risk factors, other blood laboratory parameters and urine laboratory parameters, we propose to analyze correlation(s) between delta value of outcome parameters and delta value of the efficacy parameters (e.g. urine volume, urine osmolality and plasma copeptin) with Pearson or Spearman correlation analyses.

- Outcome parameters are fasting plasma glucose and all secondary continuous outcome parameters listed in section 5.7.1 above.

We emphasize that in these correlation analyses, copeptin will be regarded both as an outcome parameter and as an efficacy parameter.

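### SAP 6.2's log-then-non-parametric rule is not reconciled with the adjusted mixed model in 5.6.2 and 5.7.2, which matters most for right-skewed secondary markers

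*SAP*

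**What the plan says.** Section 6.2 is a three-step rule. Normal data get parametric tests. Then: "If a variable deviates from normal distribution, we will log transform the variable". Finally: "If the variable still deviates from normal distribution, we will use a non-parametric test". It does not say how departure is judged, whether raw values, changes or residuals are examined, which test is used, or which outcomes are covered.

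The outcome sections specify something else. In 5.6.2: "The main analysis will be based on a linear mixed model". The dependent variable is the change in fasting glucose at 6 and 12 months, with sex, baseline glucose, treatment, visit and treatment-by-visit as fixed effects, and the output is an LS-mean difference with a 95% confidence interval. The check is given as: "Model assumptions will be assessed through visual inspection of plots of suitable regression residuals". No remedy follows if the plots look poor. Section 5.7.2 extends the model: "Cardiometabolic risk factors will be analyzed using the same method as for the primary outcome", with each factor's own baseline as covariate.

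The outcomes are listed as changes. The table in 5.6.1 has "Change of fasting plasma glucose from baseline to 6-and 12-months", and 5.7.1 has the heading "Change from baseline to 6 and 12 months of cardiometabolic risk factors". Section 4.1 (Missing data) commits to adjusting for the baseline value and says of sex: "As the randomization is stratified by sex, this covariate will be included in all outcome analyses".

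**The concern.** Section 6.2 and sections 5.6.2/5.7.2 do not refer to each other, so nothing states which prevails when an outcome looks non-normal. Section 6.1, immediately before, concerns the primary and secondary outcomes, and 6.2 follows without narrowing the scope.

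If 6.2 is applied to a listed outcome, both of its steps cause trouble. A change from baseline can be zero or negative, so it has no log for many subjects. A two-sample rank test carries no baseline value, sex or visit, which breaks the commitment in 4.1, and it yields no LS-mean difference with interval. Outcomes in one table could then answer different questions on different scales.

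The practical weight falls on the right-skewed markers, because these are the ones a normality rule would catch. Two of them have a further gap. In 5.7.1, copeptin and albumin/creatinine ratio stand under headings of their own, outside the cardiometabolic block of 18 rows that is headed as change. Section 5.7.2 assigns the mixed model to the cardiometabolic risk factors and later names the other blood and urine parameters separately. Read literally, no model is clearly assigned to these two.

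**Working it through.** **Inputs.** Difference 0.14 mmol/L, SD of the 12-month change 0.58 and 544 evaluable subjects (SAP 3.3 and 7); a 46%/54% split (SAP 5.1.3), that is 250 water and 294 control. The documents do not give the control mean change, the baseline-to-12-month correlation r, or any SD for the secondary outcomes. These are assumed below and varied.

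**The plan's own figure.** n per group = 2 × (1.96 + 0.8416)² × 0.58² / 0.14² = 2 × 7.849 × 0.3364 / 0.0196 = 269.4, so 270, as stated. With the 46/54 split the formula gives 293 + 250 = 543, against 544 stated. The inputs are sound.

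**Log step.** With control mean change m, the share with a change at or below zero is Φ(−m/0.58) in control and Φ((0.14 − m)/0.58) in water, pooled with weights 0.54 and 0.46.

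| m (assumed) | Control | Water | Pooled |
|---|---|---|---|
| +0.14 | 0.405 | 0.500 | 0.449 |
| +0.07 | 0.452 | 0.548 | 0.496 |
| 0 | 0.500 | 0.595 | 0.544 |
| −0.07 | 0.548 | 0.641 | 0.591 |
| −0.14 | 0.595 | 0.685 | 0.637 |

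So the log of the change is undefined for 45% to 64% of subjects; at m = 0 that is about 296 of 544. For any marker whose change is symmetric around zero the share is one half, and it is larger for one that falls strongly. If the measured value is logged first, the share is 0%.

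**Rank step, symmetric changes.** The gate was simulated as Shapiro-Wilk on the 12-month change (illustrative, since 6.2 names no criterion), then Mann-Whitney if rejected, otherwise the two-visit mixed model. Each cell had 2,500 trials at 250:294, with no missing visits and a residual correlation of 0.5 between visits.

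- Over 12 heavy-tailed cells with r from 0.5 to 0.7, type I error was 4.3–5.8% with the gate and 4.1–5.6% with the mixed model alone.
- Power in those cells was 81–88% with the gate and 84–91% with the model.
- A simpler one-visit ANCOVA version (1,500 trials per cell) at higher correlation reversed the order: t4 errors, r = 0.8, 0.84 for ANCOVA against 0.89 for the gate; t4, r = 0.9, 0.81 against 0.89; t5, r = 0.9, 0.84 against 0.89.

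The sign of the power difference therefore depends on tails and correlation that the documents do not give.

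**Rank step, skewed markers.** Take an assumed lognormal marker with log-SD 1.1, r = 0.8 and a 15% reduction. For a model of log visit value on log baseline:

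- residual SD = 1.1 × √(1 − 0.8²) = 0.66;
- SE = 0.66 × √(1/250 + 1/294) = 0.0568;
- effect = ln 0.85 = −0.1625, and 0.1625/0.0568 = 2.86;
- power = Φ(2.86 − 1.96) = 0.82.

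Simulation of the same case gives 0.81 for that model, 0.62 for Mann-Whitney on the change and 0.42 for ANCOVA on the raw change. Over assumed log-SD 0.5–1.1 and r 0.5–0.8, power was about 0.77–0.82 for the log-value model, 0.52–0.69 for the rank test on the change and 0.41–0.75 for the raw-change model, with type I error near 5% for all three. Since 0.75 exceeds the rank test's highest figure, while 0.42 lies below 0.62, neither of the last two is uniformly better.

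**The case against.** The strongest reply is that specific text overrides general text. Section 5.6.2 names the mixed model as the main analysis and gives it its own check, 5.7.2 extends it, and 4.1 requires baseline and sex. On that view 6.2 serves only the simple tests: the diet t-tests in 3.1.3, the paired urine differences in 5.4 and the Pearson or Spearman correlations in 5.7.2. An analyst would also normally log the marker before differencing, and then nothing is undefined. For the primary outcome this is the likelier reading and it largely stands. It does not settle the skewed secondary markers, because the SAP never says that 6.2 is so limited, gives no remedy for poor residuals, and does not say what is logged.

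Four stronger readings are tempting and are not supported.

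- That 6.2 inflates false positives. Applied mechanically it does not. If the smaller of the ANCOVA and Mann-Whitney p-values were always chosen, type I error would be 7.0–8.5% in simulation, but that is an upper bound on discretion, and nothing in the SAP proposes such a choice.
- That switching to ranks generally costs a little power. Under very heavy symmetric tails with high correlation the rank test does better.
- That every row in 5.7.1 is headed as a change. The heading covers 18 of the 20 continuous rows; copeptin and albumin/creatinine ratio are marked only as derived.
- That stating precedence is enough. On its own it would leave skewed markers on the raw-change model, which can be the weakest of the three.

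**Conclusion.** The concern holds as an unreconciled rule, with its main consequence for right-skewed secondary markers. It does not threaten the validity of the primary analysis. Type I error is not materially affected.

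The cost is precision and a consistent estimand. In the lognormal scenarios a log-value model has power of about 0.77–0.82, against 0.52–0.69 for a rank test on the change. Those sizes rest on assumed skewness, tails and correlation, because the documents give no distributional data for these markers. The 45–64% for glucose rests on the SAP's SD and difference and on an assumed control mean change between +0.14 and −0.14 mmol/L, and it applies only if the log is taken of the change. It is worth correcting before outcomes are analysed by arm.

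**What to change.** Amend 6.2 as one package:

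1. State that the 5.6.2 model, with the baseline value and sex, is the main analysis for the primary outcome and all continuous secondary outcomes, naming copeptin and albumin/creatinine ratio explicitly.
2. List in advance, from pooled baseline data, the strictly positive skewed markers. For these, log the measured visit value, use log baseline as covariate in the same model, and report a ratio of geometric means.
3. Judge normality on model residuals, and use non-parametric methods for outcomes only as sensitivity analyses.
4. Limit the parametric/non-parametric switch to the diet t-tests, the paired urine differences and the correlations.

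This costs about a paragraph of SAP text and no new data. The drawbacks are that listed markers appear as ratios beside absolute differences for the rest, a mix that is at least fixed in advance, and that some power may be lost against a rank test if changes are symmetric with very heavy tails.
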